5.5.5 Additional pertinent information after participation
N/A

5.6 Consent – Other Considerations

5.6.1 Non-English-Speaking Subjects
N/A

5.6.2 Cognitively Impaired Adults

5.6.2.1 Capability of Providing Consent
N/A

5.6.2.2 Adults Unable to Consent
N/A

5.6.2.3 Assent of Adults Unable to Consent
N/A

5.6.3 Subjects who are not yet adults (infants, children, teenagers)

5.6.3.1 Parental Permission
N/A

5.6.3.2 Assent of subjects who are not yet adults
N/A

6.0 HIPAA Research Authorization and/or Waiver or Alteration of Authorization

6.1 Authorization and/or Waiver or Alteration of Authorization for the Uses and Disclosures of PHI

Check all that apply:

- Not applicable, no identifiable protected health information (PHI) is accessed, used or disclosed in this study.** *[Mark all parts of sections 6.2 and 6.3 as not applicable]*
- Authorization will be obtained and documented as part of the consent process.** *[If this is the only box checked, mark sections 6.2 and 6.3 as not applicable]*
- Partial waiver is requested for recruitment purposes only (Check this box if patients' medical records will be accessed to determine eligibility before consent/authorization has been obtained).** *[Complete all parts of sections 6.2 and 6.3]*
- Full waiver is requested for entire research study (e.g., medical record review studies).** *[Complete all parts of sections 6.2 and 6.3]*
- Alteration is requested to waive requirement for written documentation of authorization (verbal authorization will be obtained).** *[Complete all parts of sections 6.2 and 6.3]*

6.2 Waiver or Alteration of Authorization for the Uses and Disclosures of PHI

6.2.1 Access, use or disclosure of PHI representing no more than a minimal risk to the privacy of the individual

6.2.1.1 Plan to protect PHI from improper use or disclosure

Information is included in the "Confidentiality, Privacy and Data Management" section of this protocol.

6.2.1.2 Plan to destroy identifiers or a justification for retaining identifiers

All study data will be retained indefinitely.

6.2.2 Explanation for why the research could not practically be conducted without access to and use of PHI

The study phone screener (phone screener 2) will be used to check eligibility criteria (date of birth), and when participants are screened, their contact information will be used to follow-up about scheduling and for appointment reminders. This requires that we have complete contact (name, phone number) information.

6.2.3 Explanation for why the research could not practically be conducted without the waiver or alteration of authorization

In order to screen the participants prior to inviting them into the study center, the investigators are conducting a phone screening to determine if the participants are likely to be eligible for the study.

6.3 Waiver or alteration of authorization statements of agreement

Protected health information obtained as part of this research will not be reused or disclosed to any other person or entity, except as required by law, for authorized oversight of the research study, or for other permitted uses and disclosures according to federal regulations.

[figure not shown]
The research team will collect only information essential to the study and in accord with the 'Minimum Necessary' standard (information reasonably necessary to accomplish the objectives of the research) per federal regulations.

Access to the information will be limited, to the greatest extent possible, within the research team. All disclosures or releases of identifiable information granted under this waiver will be accounted for and documented.

7.0 Study Design and Procedures

7.1 Study Design

This study is a one-site, four-arm, parallel group randomized controlled trial (RCT).

7.2 Study Procedures

7.2.1 Phone Pre-Screening

Before scheduling remote screening visit, all participants will complete initial screening questionnaires. First, participants will be directed to complete a short survey (online or over the phone) to determine eligibility for the study as part of the call routing screen protocol #2213 (Screener 1). If their information indicates potential eligibility, they will be contacted to complete Phone Screener 2 (a longer and more in-depth screening for the specific study) which is completed over the phone. Once the participant is determined eligible from Screener 2, remote screening visit will be scheduled where participants will complete the Visit Screener to determine final eligibility.

7.2.2 Final Screening Visit - Remote Visit

A Penn State Health Zoom meeting link will be emailed to participant for the previously scheduled time along with a PDF copy of the long form written consent.

Participants who meet preliminary eligibility criteria on the phone screen (Screener 2) will complete more in-depth screening measures on their smoking, substance use, medical, and psychiatric history via interview and computerized questionnaires via Zoom. Additionally, a CCQ (Clinical COPD Questionnaire, 10 items) will be administered to allow the pulmonologist on the study team to review changes in health status to lung function, degree of dyspnoea and (change in) functional capacity. This will be administered at all study visits. Participants will then complete the B-SIT test. At the conclusion of the visit, eligible participants will be instructed to abstain from using any tobacco products for 14 hours prior to the next visit. Participants will also be instructed to eat before their next visit. Cigarettes per day will be recorded on a daily log and participants will receive a daily REDCap survey link via text message using the Twilio service to enter their use information daily. Participants will be instructed on how to complete the survey. Participants who are unable or unwilling to receive study text messages will track their cigarette use on the paper log only and report their use to the researchers at each contact. All participants will be given a manual on how to use the study provided e-cigarette to review before being given the study device at their next visit.

7.2.3 Randomization/Pre-Conditioning fMRI Visit (Day 0) – In Person/Remote

Participants will sign their long form written consent at this visit prior to any further study procedures.

Exhaled breath CO (eCO) will be measured at the start of the visit. A urine sample will also be collected and tested for cotinine using the NICCheck cotinine test and pregnancy if participants are of child bearing potential. Eligible participants will then be randomized to one of the four conditions and asked to complete the baseline assessments. This includes the standardized smell test (B-Sit), adverse events assessment and computerized questionnaires of cigarette use, cigarette dependence, liking, and withdrawal as indicated in Table 1. Some of the measures can be done remotely via Zoom, others will need to be completed in person. The remote assessments will be conducted via a Zoom session within 3 days following the scheduled in-Person MRI. The remote visit will only occur after written consent has been obtained. This is being done to limit the amount of face-to-face time during study visits.

Then, participants will complete the fMRI odor cue-reactivity task in the MRI scanner lasting approximately 45 minutes. During the scan, participants will be administered four flavors in separate 4 minutes blocks for eight runs. The flavors will be delivered to the participant's nostrils via tubing from the olfactometer machine. The release of the flavors will be timed with participants' natural rate of respiration and randomized across blocks. At the end of this visit participants will be given the ECIG device and 4-week supply of their randomly assigned flavor cartridges (approximately 2 cartridges/day) and instructed on how to use the device.

Participants will be instructed to take at least 50 puffs per day from the ECIG device to replace conventional cigarette smoking. The participant will be instructed to bring back all used and unused cartomizers to the study center. ECIG puffs per day and cigarettes per day will be recorded on a daily log. Participants will receive a daily REDCap survey link via text message using the Twilio service. Participants will be instructed on how to complete the survey and will be provided with a paper log to tally their cigarette use throughout the day. Participants who are unable or unwilling to receive study text messages will track their cigarette use on the paper log only.

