3.3 Early Withdrawal of Subjects

3.3.1 Criteria for removal from study

The Principal Investigator reserves the right to remove a participant from the study for any reason, based on their discretion.

Early Withdrawal Criteria Prior to Randomization: Participants who met any criteria below at Visit 2 will be considered for withdrawal prior to randomization:

1. Starting nicotine replacement therapy (e.g., patch, gum, lozenge, inhaler, nasal spray, Zyban, Chantix)
2. Use of other non-cigarette tobacco products in the past 7 days
3. Reporting a quit attempt in the past 7 days
4. Participant is not able to attend their Visit 2 Randomization visit within the study window.

General Withdrawal Criteria

1. Missing their study visit window: If a participant misses their study visit window, the participant will be considered for withdrawal from the study.
2. Not maintaining ECIG and cigarette use diary
3. New pregnancy: Participants who report a new pregnancy at any point during the study will be withdrawn.
4. Suicide attempt: If at any time during the study it is discovered that a participant has made a suicide attempt, they will be withdrawn from the study.
5. Cardiovascular disease (CVD) event requiring inpatient hospitalization: CVD typically includes MI (heart attack), PTCA (angioplasty/stenting), bypass surgery, stroke, peripheral vascular disease (arterial blockages in arms or legs leading to procedure or surgery). Less common CVD problems would be new cardiac arrhythmias (e.g., new atrial fibrillation) or new valvular disease (e.g., mitral or aortic regurgitation).
6. DVT/PE (deep vein thrombosis/pulmonary embolism, i.e., blood clots in the venous system) requiring inpatient hospitalization.
7. Psychiatric Inpatient Hospitalization: A participant will be withdrawn if he/she reports an inpatient hospitalization for psychiatric reasons at any time during participation in the study.
8. Participant choice: Participants may choose to remove themselves from the study by informing the research team in writing, by phone call or in person at any point during the study. If they choose to remove themselves from the study, they will not receive any further contact from the study center.
9. Adverse events related to ECIG use: Adverse events will be monitored at every study visit.
10. Worsening substance abuse in which the participant is behaving inappropriately at visits or demonstrates an inability to continue with the study.

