3.3.2 Follow-up for withdrawn subjects

If participants are withdrawn from the study for any of the reasons noted above prior to randomization, they will be replaced until a total of 56 participants have been randomized to the study. Reasons for withdraw will be ascertained from subjects who withdraw from the study. In addition, among all participants who choose to withdraw, we will attempt to confirm their withdrawal and reason for withdrawal in writing (via mail or email).

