4.2 Recruitment process

4.2.1 How potential subjects will be recruited.

Interested volunteers calling the study center number will first complete the eligibility script and questions for IRB STUDY00002213 (screener 1). If a participant's responses match this study's specified inclusion criteria they will be forwarded to research staff for further phone screening (phone screener 2). Subjects that were unable to be reach by phone will have an email sent to them asking them to contact us via email or phone. A draft of the email will be uploaded to CATS.

Recruitment materials are included in IRB STUDY00002213.

4.2.2 Where potential subjects will be recruited.

Refer to IRB STUDY00002213 Call Routing Screener.

4.2.3 When potential subjects will be recruited.

Starting 2019 and running till 2024.

4.2.4 Describe the eligibility screening process and indicate whether the screening process will occur before or after obtaining informed consent. Screening begins when the investigator obtains information about or from a prospective participant in order to determine their eligibility. In some studies, these procedures may not take place unless HIPAA Authorization is obtained OR a waiver of HIPAA Authorization when applicable for the screening procedures is approved by the IRB. [For FDA regulated studies, consent for any screening activities would need to be obtained prior to screening unless specifically waived by the IRB.]

Verbal informed consent will be collected over the phone prior to screener 2. Potential eligible participants will be invited to take part in a remote visit where additional eligibility screening will occur. Written informed consent will be obtained before in-person randomization/MRI visits will begin.

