7.4.6.3 Preparation and Dispensing

The unblinded study staff will be responsible for filling the cartomizers with the appropriate nicotine concentration (0mg/ml or 18 mg/ml) and flavor (tobacco or strawberry vanilla) in a biological safety cabinet. Filled cartomizers will be stored in bottles/bags with child-proof caps. Once filled, unblinded staff will then put cartomizer-containing bottle into ECIG kits

labelled with unique identifiers in order to track bottles and maintain blinding. Unblinded staff will appropriately package kits for the participants. At the randomization visit (Visit 2), participants will be randomly assigned a Randomization ID that matches a kit number. The blinded research assistants will not be involved in the packing and labelling of the kits. The blinded research assistant will be told what participant is assigned to which Randomization ID, which will maintain the blind.

7.4.6.4

Return or Destruction of the Test Article

Participants will be permitted to keep their ECIG device at the end of the study. Participants will be required to return all used and unused cartomizers to the research assistant at each clinic visit using provided containers/bags. Participants will not keep unused cartomizers at the end of the study. If a participant is withdrawn for medical reasons (CVD event), they will be asked to return their device/cartomizers via a pre-paid envelope to the study center.

7.4.6.5

Prior and Concomitant Therapy

Concomitant medications will be collected regularly throughout the trial to serve as covariates during analysis and to monitor participant health conditions. Medications related to certain medical conditions that are exclusions to the study, such as COPD and current heart conditions, will serve to alert the study staff of the presence of these conditions during screening.

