8.0 Subject Numbers and Statistical Plan

8.1 Number of Subjects

Up to 75 subjects may be enrolled in this study in order to have 56 randomized subjects. We will continue to consent participants to the study until we reach 56 randomized subjects.

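### Visit 2 is written with randomization before the baseline scan; assigning the kit after the scan would be a cheap, low-priority improvement, because a failed scan then uses one of the 56 places and is not replaced.

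*Combined protocol and SAP*

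**What the plan says.** Section 7.2.3 describes Visit 2 in this order: written consent, exhaled CO and urine tests, randomization, baseline assessments, scan, hand-over.

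- Randomization: "Eligible participants will then be randomized to one of the four conditions and asked to complete the baseline assessments".
- Scan: "Then, participants will complete the fMRI odor cue-reactivity task in the MRI scanner lasting approximately 45 minutes".
- Hand-over: "At the end of this visit participants will be given the ECIG device", together with the assigned cartridges.

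Sections 7.4.5 and 7.4.6.3 fix the visit but not the moment within it. At Visit 2, "participants will be randomly assigned a Randomization ID that matches a kit number".

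On numbers, section 3.3.2 says that people withdrawn "prior to randomization, they will be replaced until a total of 56 participants have been randomized to the study". Section 8.1 adds "Up to 75 subjects may be enrolled in this study in order to have 56 randomized subjects" and stops consenting at 56 randomized. Section 7.4.3 sets a 1:1:1:1 ratio, which is 14 per arm.

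On the endpoint, section 8.3 forms the change image by subtracting the baseline image from the post-conditioning image. Section 7.2.10 delivers the same four odors to every participant.

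**The concern.** No step before hand-over needs the allocation: the scan stimuli are the same in all arms, and the kits are packed and numbered beforehand. Randomizing before the scan therefore gains nothing that the documents state. It does move any baseline scan failure from the side of the line where the plan replaces people to the side where it does not.

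Failures are foreseeable. Section 10.5 names claustrophobia and discomfort, lets the participant stop the scan at any time, and repeats the MRI safety check at the scan visit without saying that this precedes randomization. The documents do not say whether a stopped scan may be repeated, whether a partial scan counts, or how a missing baseline image is handled. At stake is the number analysed per arm in Aims 2 and 3, which starts at 14 and has no stated allowance for loss after randomization.

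**Working it through.** **1. The counting.** Let R be the number who reach the baseline scan and f the share whose scan fails and is not repeated.

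- As written, the number with a baseline scan is min(R, 56) × (1 − f).
- With the kit assigned after the scan, it is min(R × (1 − f), 56).

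The second is never smaller than the first. The unused reserve is 75 − 56 = 19 places at most.

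**2. The plan's own power figures (section 8.2).** The plan states about 50%, 60% and 90% for a medium effect. It gives neither group sizes nor sidedness. I take d = 0.5 and use the noncentral t distribution.

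- 14 vs 14, one-sided .10: 50.8%, which matches the 50%.
- 28 vs 28, two-sided .10: 58%, close to the 60%.
- Within-subject change, n = 56, two-sided .05: 95.7%, against a stated 90%.

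The point here is about order and counting and does not depend on which inputs the plan used.

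**3. Effect of unreplaced failures.** The documents give no failure rate, so f is an assumption, shown from 1% to 15%. Each group has n × (1 − f) people; d = 0.5, alpha .10. Aim 3 compares 14 with 14. The Aim 2 nicotine comparison is 28 with 28 if the flavors are pooled. The last column is the chance that two independent Binomial(14, f) counts of failures differ by 2 or more.

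| f | Expected failures of 56 | 14 vs 14, two-sided | 14 vs 14, one-sided | 28 vs 28, two-sided | 28 vs 28, one-sided | Two arms differ by ≥ 2 |
|---|---|---|---|---|---|---|
| 0 | 0 | 36.2% | 50.8% | 58.0% | 71.7% | 0 |
| 1% | 0.6 | 36.0% | 50.5% | 57.7% | 71.4% | 1.5% |
| 2% | 1.1 | 35.7% | 50.3% | 57.3% | 71.1% | 4.8% |
| 5% | 2.8 | 35.0% | 49.4% | 56.2% | 70.1% | 17% |
| 10% | 5.6 | 33.7% | 48.0% | 54.2% | 68.4% | 33% |
| 15% | 8.4 | 32.4% | 46.6% | 52.2% | 66.6% | 42% |

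**4. Scan attempts needed after the change.** 56/(1 − f), rounded up: 56/.95 gives 59 and 56/.85 gives 66. That is 3 to 10 more attempts, and the reserve falls from 19 to 16 (75 − 59) or 9 (75 − 66). Extra people with a baseline scan: 56 − 53.2 = 2.8 at 5%, and 56 − 47.6 = 8.4 at 15%.

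**5. Payments (section 13).** A completer earns 4 × $40 + 2 × $20 + $20 = $220. After the change, a failed scan at Visit 2 ends participation at 2 × $40 = $80. As written, a randomized person with a failed scan earns $80 if they leave then. If they stay, they earn $180 without a Day 28 scan or $200 with one.

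- 5%, after the change: 56 × 220 + 3 × 80 = $12,560. As written: 53.2 × 220 + 2.8 × (80, 180 or 200) = $11,928, $12,208 or $12,264. Difference: $632, $352 or $296.
- 15%, after the change: 56 × 220 + 10 × 80 = $13,120. As written: 47.6 × 220 + 8.4 × (80, 180 or 200) = $11,144, $11,984 or $12,152. Difference: $1,976, $1,136 or $968.

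**6. If recruitment or the cap binds, at f = 15%.** With R = 60: 60 × .85 = 51 with a baseline scan, against 56 × .85 = 47.6 as written. With R = 56: 47.6 either way, but about 48 randomized instead of 56.

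**The case against.** **The loss is small and may not occur.** This is a proof-of-concept study, and section 8.2 says that its between-subject analyses look for trends. At 1–2% failure the power loss is half a point or less for 14 vs 14, and any figure above that rests on a rate that the documents do not supply. If failed scans are repeated successfully, nothing is lost. All of this stands, and it is why the point is low priority.

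**Section 7.2.3 is not strictly chronological.** Ahead of the scan it mentions remote assessments that take place up to 3 days after the MRI. Practice may already differ from the text. That is fair, but no other section places randomization after the scan, so one clarifying sentence is still needed.

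**A failed scan is not a wasted place.** A reader might infer that the participant is lost to the trial. The documents do not support that: nothing withdraws such a person, and cigarette dependence, ECIG dependence and ECIG liking and satisfaction (section 1.3) need no scan. The loss is confined to analyses that use the baseline image.

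**The withdrawal rules are already broad.** Section 3.3.1 says "Participants who met any criteria below at Visit 2 will be considered for withdrawal prior to randomization", and its four listed criteria do not include scan failure. A reader might conclude that a fifth is required. It is not: the same section lets the Principal Investigator remove a participant for any reason and allows withdrawal by choice, and section 3.3.2 replaces anyone withdrawn for those reasons before randomization. Once the order changes, the rule already reaches failed scans. As written it does not, because the removal comes after randomization.

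**Bias.** A reader might also infer that the order biases the arm comparison. The documents give no ground for that: the failure happens before any product is handed over, in participants blinded to arm, so it should not depend on arm.

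**Conclusion.** The point holds as a low-severity, low-cost improvement. As section 7.2.3 is written, a baseline scan that fails and is not repeated uses up one of 14 places in an arm, and the replacement rule does not refill it. The consequence is lost precision and some arm imbalance in Aims 2 and 3. It is negligible at 1–2% failure. At 15% it is about 4 power points for 14 vs 14 and 6 for 28 vs 28, two-sided.

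The size rests on three assumptions: d = 0.5, alpha .10 and the failure rate. The order and the counting rest on the text alone.

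**What to change.** State in section 7.2.3 that the Randomization ID and kit number are assigned after the baseline scan is completed and just before hand-over. Define completed in advance by run count, for example at least one run each of tobacco, strawberry vanilla and rose, so that it can be judged on the day without image review. Say whether a stopped scan may be repeated. The rules in sections 3.3.1 and 3.3.2 then cover failed scans within the cap of 75.

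Also state who counts toward the 75. Section 4.2 says "Verbal informed consent will be collected over the phone prior to screener 2". If enrolment is counted from that consent, the usable reserve is smaller than 19.

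Cost at an assumed 5–15% failure: about 3–10 more baseline scan attempts, up to 3–8 more Day 28 scans, and roughly $300–$2,000 in participant payments, depending on whether people with a failed scan would otherwise have stayed. If the cap binds, fewer people are randomized and available for the secondary endpoints, though never fewer with a baseline scan. The change does nothing for complete scans of poor quality or for dropout before Day 28.

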7.2.4 Conditioning Phase Check-in Visit (Day 14 ± 7 days) - Remote

Participants will take part in a remote visit via Zoom to report their ECIG use and cigarettes per day (CPD) (collected in the daily logs). Participants will complete the measures outlined in Table 1. Participants will complete an adverse events assessment and discuss challenges to using their e-cig daily and study staff will assist in problem solving barriers to compliance. At the end of the visit participants will be instructed to remain abstinent from all tobacco products including their ECIG for 14 hours prior to the next study visit and to eat before their next study visit.

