7.2.5 Post-Conditioning fMRI Visit (Day 28 ± 7 days) – In Person/Remote

Participants will attend a final visit to complete biomeasures, computerized surveys, the adverse events assessment, and the same fMRI tasks as the baseline MRI visit as indicated in Table 1. Some of the measures can be done remotely via Zoom, others will need to be completed in person. The remote assessments will be conducted via a Zoom session ± 3 days of the scheduled in-Person MRI. This is being done to limit the amount of face-to-face time during study visits. eCO will be measured and urine will be collected for cotinine and pregnancy tests. At the end of the visit, participants will be debriefed and counseled on smoking cessation. All participants will be given a copy of the Surgeon General's booklet 'How Tobacco Smoke Causes Disease' (SEE ATTACHMENT: Surgeon General's Booklet).

Table 1: Measures Table (Black X – In Person; Green X – Remote)

	Final Screening	Randomization/ Pre-Conditioning fMRI	Check-In	Post- Randomization fMRI
Visit	1	2	3	4
Day	-7	0	14	28
QUESTIONNAIRES				
Visit Screener	X			
Tobacco Use History	X			
Name Registry	X			
MRI Safety Form	X	X		X
Demographics	X			
Medical History	X			
Concomitant Medications	X	X	X	X
Adverse Event Assessment		X	X	X
Cigarette Details	X			
CCQ (Clinical COPD Questionnaire)	X	X	X	x
Alcohol Audit-C	X			
NIDA Quick Screen	X			
Environmental Smoke Questionnaire	X			
MINI Psychiatric Interview	X			
Daily Smoking and ECIG Use Logs	X (cigarette only)	X	X	X
Cigarette Dependence (Fagerstrom and Penn State Cigarette Dependence Index)		X	X	X
Minnesota Withdrawal Scale		X	X	X
Craving		X	X	X
Cigarette liking scale		X	X	X
ECIG Use History	X	X	X	X
ECIG evaluation scale			X	X
ECIG Side Effects			X	X
ECIG dependence			X	X
ECIG Perceived Health Risk			X	X
ECIP Patterns of Use			X	X
Perceived Benefits and Harms of Using ECIG		X		X
PROCEDURES				
B-SIT Smell Test		X		
fMRI Cue-Reactivity Task in Scanner		X		X
BIOMEASURES				
Pregnancy Test		X		X
Exhaled CO		X		X
Urine Sample Collection		X		X
NICCHECK Rapid Cotinine Test		X		X

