7.3 Duration of Participation

All participants will be in the study for a period of at least 5 weeks but no more than 8 weeks and will attend 2 in-person clinic visits at the study center. The randomization/pre-conditioning visit (Visit 2), remote check in (Visit 3) and post-conditioning visit (Visit 4), will happen within a 4 week period.

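### Remote Visit 2 baseline questionnaires can fall up to 3 days after the randomized product is dispensed, with no earlier value to fall back on

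*Combined protocol and SAP*

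**What the plan says.** Section 7.2.3 randomizes participants at Visit 2 and then asks for baseline assessments, including "computerized questionnaires of cigarette use, cigarette dependence, liking, and withdrawal as indicated in Table 1". The next step it describes is the scan. It also allows some of the measures to be done by Zoom, in a window that opens only after the scan: "The remote assessments will be conducted via a Zoom session within 3 days following the scheduled in-Person MRI". It adds that this remote part must wait for written consent.

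On dispensing, the same section says: "At the end of this visit participants will be given the ECIG device and 4-week supply of their randomly assigned flavor cartridges". The use instruction follows: "Participants will be instructed to take at least 50 puffs per day from the ECIG device to replace conventional cigarette smoking".

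At Visit 4 the window is different (section 7.2.5): "The remote assessments will be conducted via a Zoom session ± 3 days of the scheduled in-Person MRI".

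Abstinence is tied to the visit and is not mentioned for the Zoom session. Before Visit 2, "eligible participants will be instructed to abstain from using any tobacco products for 14 hours prior to the next visit" (section 7.2.2). Before Visit 4, participants are to "remain abstinent from all tobacco products including their ECIG for 14 hours prior to the next study visit" (section 7.2.4).

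Table 1 separates in-person from remote items by the colour of the X. Section 9.7 plans paired tests of change from baseline in cigarettes per day, CO and subjective measures.

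**The concern.** A baseline should describe the participant before the randomized product has had a chance to act. Here the post-scan Zoom session comes after both randomization and dispensing. A questionnaire placed in that session may already reflect early use of a product that differs by arm in nicotine (0 or 18 mg/ml) and flavor.

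Withdrawal and craving raise a second problem. The scan-day state follows 14 hours of abstinence, while a Zoom session one to three days later carries no abstinence instruction. A change score could then mix two states.

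What is at stake is the interpretation of change from baseline in the Visit 2 questionnaires, chiefly cigarette dependence, which section 1.3 names as a secondary endpoint.

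**Working it through.** The plan states no figure on this point, so there is none to reproduce. The check is of sequence, then of dates.

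**1. Can dispensing come after the Zoom session?** Section 7.3 says that participants "will attend 2 in-person clinic visits at the study center". Those are the two scan visits. Section 7.4.6.3 assigns the kit at the randomization visit, and no section describes shipping a device to a participant. The handover therefore belongs to the in-person part of Visit 2, and the Zoom session follows it. No section asks participants to delay first use until that session.

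**2. Which questionnaires could be exposed?** From Table 1 and sections 1.3 and 7.2.10:

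| Measure | Visit 1 | Visit 2 | Named secondary endpoint | Could have a late baseline |
|---|---|---|---|---|
| Cigarette dependence | no | yes | yes | yes, if remote |
| Withdrawal, craving, cigarette liking | no | yes | no | yes, if remote |
| Perceived benefits and harms | no | yes | no | yes, if remote |
| ECIG dependence, ECIG evaluation scale | no | no (start at Visit 3) | yes (ECIG dependence, liking, satisfaction) | no |
| Flavor liking | no | rated at the end of the scanner task | yes | no, precedes dispensing |
| CO, cotinine, fMRI | no | yes, in person | fMRI is primary | no |

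Cigarette dependence, withdrawal, craving and cigarette liking are also scheduled at Visit 3, which is wholly remote. They can be given by Zoom, but this does not show how they are coded at Visit 2.

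**3. Exposure before a remote baseline.** Formula: days since dispensing × 50 instructed puffs per day.
- Same day: about 0
- 1 day: 1 × 50 = 50 puffs, 1/28 = 3.6% of the 28-day conditioning period
- 2 days: 2 × 50 = 100 puffs, 2/28 = 7.1%
- 3 days: 3 × 50 = 150 puffs, 3/28 = 10.7%

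These are instructed amounts (a daily minimum), not observed use.

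**4. Interval between baseline and final questionnaire.** The scan interval from section 7.2.5 is 28 − 7 = 21 to 28 + 7 = 35 days. The Visit 4 Zoom session can fall from day 21 − 3 = 18 to day 35 + 3 = 38, and the Visit 2 session from day 0 to day 3. The questionnaire interval is therefore 18 − 3 = 15 to 38 − 0 = 38 days.

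**5. Which analyses use these values?** Aims 1 to 3 in section 8.3 test fMRI contrasts only. The exploratory aim takes change in craving, satisfaction and dependence from the 2-week check-in to the final visit, so Visit 2 values do not enter. It also cites a baseline ECIG liking value, for which Table 1 shows no Visit 2 questionnaire. That leaves the paired tests in section 9.7.

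**The case against.** The strongest reply is that the plan does say which items are remote: Table 1 marks each one by colour. If the dependence, withdrawal, craving, liking and perceived-harm rows are marked in-person at Visit 2, no baseline questionnaire is late. Section 7.2.3 speaks only of some measures being remote, and its main narrative runs from assessments to scan to dispensing. The remote part is also a deliberate choice to limit face-to-face time, and it follows the in-person visit because written consent is signed there.

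Much of this stands. The coloured table settles which items are affected, and the concern lapses for any item marked in-person. It does not settle the conflict inside section 7.2.3, where baseline assessments precede the scan in one sentence and may follow it by up to 3 days in another. The need for consent does not require the delay either, since a survey can be completed on site after signature.

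A reader might infer three stronger points that the documents do not support.
- **Secondary-endpoint baselines in general are compromised.** Of those named, only cigarette dependence has an exposed Visit 2 questionnaire.
- **Arm comparisons are biased toward no difference.** No between-arm or baseline-adjusted questionnaire analysis is planned. The direction is also open: early product effects absorbed into baseline could shrink a change, while a non-abstinent baseline set against an abstinent final value could enlarge a change in craving or withdrawal.
- **150 puffs far exceeds the 11 pairings cited in section 2.1.** Those are pairings of cues with smoking and concern physiological cue-reactivity. They are neither puffs nor questionnaire scores, and the baseline scan precedes dispensing.

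**Conclusion.** The point holds in a limited form. As written, section 7.2.3 allows any Visit 2 questionnaire coded remote to be recorded after 0 to about 150 instructed puffs of the randomized product. No Visit 1 value exists for the candidate scales, so the change from baseline in section 9.7 may not start from a pre-exposure value. Questionnaire change can span 15 to 38 days, against 21 to 35 days for the scans.

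This rests on three assumptions: that at least one of the candidate rows is coded remote at Visit 2, that baseline in section 9.7 means the Visit 2 value, and that participants start using the product when told to. The documents give no standard deviation or expected change for these scales, so neither the size nor the direction of bias can be computed. The primary fMRI endpoint, CO, cotinine, in-scanner flavor liking and the exploratory changes from Visit 3 to Visit 4 are untouched.

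**What to change.** - **Section 7.2.3:** require every questionnaire used as a baseline value to be completed after written consent and before the device is dispensed, for example as a self-completed REDCap survey at the in-person visit. Leave only history-type items for the later Zoom session. Reconcile the assessments-then-scan order with the post-scan window, and check the coding in the coloured Table 1. Instructed exposure before baseline then falls from as much as 150 puffs to 0.
- **Withdrawal and craving:** collect each pair of visits being compared in the same abstinence state, and record the time of each questionnaire. Requiring abstinence for all Visit 4 questionnaires would not achieve this. The exploratory aim compares Visit 4 craving with Visit 3, which has no abstinence instruction, whereas a pre-dispensing Visit 2 value follows 14 hours of abstinence. The plan should say which Visit 4 reading serves which comparison.
- **Section 9.7:** define baseline, and state how a value recorded after dispensing is handled.

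The cost is a few more minutes on site, against the plan's stated wish to limit face-to-face time.
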